4 STUDY DESIGN

This section describes the model and design of the intervention study. The study will utilize a multi-site, double-blind, parallel arm, community-based randomized trial design (Phase 3).

4.1 Study Participants

Subjects will be parents/caregivers and their children in grades K-4 in one of three Counties: Cuyahoga County (East Cleveland City School District (ECCSD, Cleveland, OH) and Bedford City School District (BCSD, Bedford, OH)); Cowlitz County (CC, WA); and Lewis County (LC, WA); (See Table 4.1.1 below). The study will be offered to all caregivers and their children including those children with special health care needs. Parent/caregivers and children will be enrolled in the study upon signing the consent/assent form and completing the recruitment and contact form. All enrolled children will receive a dental screening at the beginning of the school year. Following the screening, only parent/caregivers whose child has a tooth with an International Caries Detection and Assessment System (ICDAS) active lesion score of 2 or greater will be randomized and continue further participation in the trial. Caregivers with multiple children in K-4 will receive the same intervention assignment.

Table 4.1.1 School District Information

County	School District	Elementary Schools	K-4 Enrollment
Cuyahoga Co.	East Cleveland City SD	Caledonia, Chambers, Mayfair, Superior	889
	Bedford City SD	Central, Glendale, Columbus, Carywood	1274
Cowlitz Co.	Kelso SD.	Catlin, Wallace	1122
	Longview SD.	Kessler, St. Helens	
Lewis Co.	Central SD.	Jefferson Lincoln	586
	Winlock SD.	Winlock Miller	

4.2 Model and Design

Figure 4.2.1 shows the study model for the intervention. The experimental intervention will be based upon the Common Sense Model of Self-Regulation (CSM: Leventhal et al. 2003) to address parent/caregiver illness perception and navigation of resources to increase receipt of dental care during a 7-month follow-up period for children with restorative dental needs. In this five arm study a CSM referral letter alone, a CSM referral letter plus Dental Information Guide (DIG), a reduced CSM referral letter alone, and a reduced CSM referral letter plus DIG will each be compared to a modified standard referral letter (based on November 2007 guidelines for Oral Health Screening in

Ohio Schools) to increase receipt of dental care among inner-city urban African American, and rural Hispanic and White elementary school children.

[figure not shown]

Figure 4.2.1 Conceptual model describing the pathway mechanisms of the proposed new interventions

Figure 4.2.1 illustrates the pathway through which the referral approaches (CSM referral letter alone, CSM referral letter + DIG, reduced CSM referral letter alone, reduced CSM referral letter + DIG, and modified standard letter) are intended to result in action by the caregiver. The child's receipt of care will be mediated by changes in caregiver's illness perception and behavioral intention, which will result from the interventions. The first mediator, caregiver's illness perception is comprised of five constructs such as identity, cause, consequences, timeline, and controllability. The second mediator is caregiver's behavioral intention (Ajzen, 1991), i.e. their motivation or intention for taking their child to the dentist. Intention to initiate an action is also the first step in action planning. The moderating variables in the model are caregiver's literacy, self-efficacy, dental fear, perceived stress, and dental insurance status. Additionally, to test other causal explanations for the effect of the intervention letters on receipt of dental care, measures from the health belief model (HBM: caregiver beliefs and attitudes, self-efficacy) and theory of planned behavior (TPB: subjective norms) theories will also be considered as mediators in this conceptual model. Additional mediational analysis will be conducted to explore alternative causal explanations.

A description of the five study arms is as follows:

Arm 1 (N=204): The first arm is the CSM referral letter alone. The letter text includes the cognitive dimensions of the CSM (identity, cause, consequences, timeline, and controllability). The letter has been tested for readability and clarity with caregivers of K-2 children. The referral letter will be given to the caregivers in their preferred language (English or Spanish).

Arm 2 (N=204): The second arm is the CSM referral letter plus DIG to reinforce/change illness perception, knowledge about dental caries, and resources to seek care. The DIG is a brochure with

illustrations which provides myths and facts about dental caries, hints for getting dental care, making appointments and Medicaid access, transportation and dentist availability resources. While the general information on dental caries is similar for both sites, other resource information on how to seek care and a list of dentists is adapted to the specific site.

Arm 3 (N=24): The third arm is the reduced (removing text corresponding to “timeline”) CSM referral letter alone. The referral letter will be given to the caregivers in their preferred language (English or Spanish). The letter includes the remaining cognitive dimensions of the CSM (identity, cause, consequences, and controllability). While the last line (timeline construct) reinforces the core issues (baby teeth’s impact on adult teeth and the disease’s chronic nature), the text and constructs leading up to the last line is equally important. We think that this final message is fundamental to the intervention letter and this version will allow an estimate of the effect of the “timeline” text itself.

Arm 4 (N=24): The fourth arm is the reduced CSM referral letter plus DIG to reinforce/change illness perception, knowledge about dental caries, and resources to seek care. The reduced DIG is a brochure with illustrations that provides myths and facts about dental caries, hints for getting dental care, making appointments and Medicaid access, transportation and dentist availability resources. As with the reduced letter, text and illustrations related to the “timeline” construct have been removed in the reduced dental information guide. This version will allow for an estimate of the effect of the “timeline” text and illustrations. While the general information on dental caries is similar for both sites, other resource information on how to seek care and a list of dentists is adapted to the specific site.

Arm 5 (N=204): The fifth arm (control) is the modified standard letter (based on November 2007 guidelines for Oral Health Screening in Ohio Schools). This letter is consistent with others used across the country and will be used in both the Ohio and Washington sites.

All letters will be sent home with the child on the day of the screening and mailed to the caregiver’s address within 24 hours. The address will be obtained during recruitment and verified with the school secretary.

A description of the recruitment, enrollment, randomization, and follow-up is below:

Caregivers will be recruited at the beginning of the school year and complete baseline forms (consent form, Illness Perception Questionnaire-Revised for Dental (IPQ-RD) questionnaire, and caregiver questionnaire) prior to dental screening and randomization (Figure 4.2.2). Children in K-4 whose parents have consented/assented will receive a screening exam in early October 2015. Caregivers whose children have no cavities or who have emergent needs will not participate further in the clinical trial. The baseline data from discontinued child and caregiver participants will be used only for baseline descriptive comparisons.

At the same time following screening exams eligible caregivers of children with restorative referrals will be randomized. Caregivers will be followed at 2 time points: 2 weeks after the receipt of the intervention letter and 2 weeks prior to the final (exit) study visit examinations in May 2016 (approximately 7 months after the initial dental exam). At both time points caregivers will complete the IPQ-RD and the caregiver questionnaire. A small sub-sample of 60 caregivers will be randomly

sampled from arms 1, 2 and 5 (20 per arm), to complete the IPQ-RD 1 month after enrollment for reliability purposes. All questionnaires will be mailed to the home address and asked to be returned to the class-room teacher or the outreach staff. Further, outreach staff will ensure that the caregivers received and returned the materials through follow-up calls. The schedule and scripts for the call are contained in the MOP (Table 6.1 and Appendix 6). Children will have a follow-up dental exam in May 2016.

[figure not shown]

Figure 4.2.2 Flowchart for Recruitment, Enrollment, and Randomization

5 STUDY ENROLLMENT AND WITHDRAWAL

5.1 Subject Inclusion Criteria for Enrollment

Inclusion Criteria: Inclusion criteria for Parents/Caregivers and their children for enrollment:

- Provide signed and dated consent form (also assent form for children 7 and older)
- Willing to comply with all study procedures and be available for the duration of the study
- Male or female child, grades K-4
- Child in good general health as evidenced by parent report (including children with special health care needs). Caregivers will indicate on the Recruitment and Contact Form if their child has any major medical problems or any cognitive or developmental disorders that would preclude them from participating in the dental exam.

Additional Subject Inclusion Criteria for study continuation and randomization:

- Caregivers will be randomized if their child has tooth with an International Caries Detection and Assessment System (ICDAS) active lesion score of ≥ 2 . Caregivers with multiple children in K-4 will receive the same intervention assignment.

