3.2.1 Primary Outcome Measures

The primary outcome will be receipt of dental care based on a change determined by clinical examination between baseline and follow-up at study exit (7 months after baseline). Please see MOP Section 5.2 for details of dental exam and criteria.

In addition, other proximal surrogate outcomes from the caregiver questionnaire will also be assessed. These questions include: whether the child visited the dentist after the dental screening, the name of the dentist/dental clinic, whether an appointment was made or not, whether the child completed the needed dental treatment, the number of visits that were made to complete dental treatment, and if they did not complete the treatment the reasons why they did not complete the treatment.

Examiner Training and Calibration: Exams will be conducted in a portable dental chair in the schools by a trained/calibrated examiner. [name] will train/calibrate the examiners in the ICDAS protocol in a 4-day central training session. Detailed caries assessment and examiner training, calibration and reproducibility protocols are in the MOP (Section 5.2). Examiners will not utilize dental radiographs. At follow-up, the examiner will not have access to the results of the first examination to avoid detection bias.

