7.2 Baseline Dental Screening

Baseline Dental Screening Visit (Visit 1, Day 0-5)

- Obtain assent of child prior to dental screening examination.
- Perform initial child dental screening examination at child's respective elementary school.
- Record results of dental screening examination.
- Randomize caregivers of children with restorative referral outcome on screening to 1 of 5 study arms.
- Send referral letter packets to caregiver with child and by mail.
- Telephone contact with caregivers (within 48 hours of screening examination) to confirm receipt of referral letter packet.

- Resend referral letter packets to caregivers as necessary.
- Follow-up telephone contact with caregivers to confirm receipt of secondary letter.

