8 STUDY PROCEDURES/EVALUATIONS

The following are the various study procedures and evaluations that will be done during the study:

Administration of questionnaires (IPQ-RD and caregiver questionnaires including demographic information) for caregiver and child information (See Section 3.2, Table 3.2.1; see Appendix C): Caregivers will be asked to complete questionnaires at three time points (baseline prior to screening, 2 weeks after the dental screening examination, and at the end of the school year).

Dental examinations for baseline caries status and primary study outcome: Exams will be performed on the children whose caregivers have consented to their participation. The dental examinations will be done according to the standard caries detection and assessment system termed ICDAS (International Caries Detection and Assessment System). The initial examination (approximately 2 months after the beginning of the school year) will determine a child's need for restorative care which is an inclusion/exclusion criterion for study continuation and randomization. The final examination (approximately 1 month prior to the end of the school year) will be used for the primary study outcome for children enrolled in the RCT.

Administration of the intervention (referral letters) (See Section 6 – Study Intervention): The letter will be sent home with the child and mailed to the caregiver. Confirmation that the letter was received will be obtained through telephone contacts.

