12.2 Sample Size Considerations

The primary aims are to compare dental care receipt among the five intervention groups, overall and separately for each study site (Ohio and Washington).

The five intervention groups are:

Arm 1: CSM referral letter alone (N=204)

Arm 2: CSM referral letter + DIG (N=204)

Arm 3: Reduced CSM referral letter alone (N=24)

Arm 4: Reduced CSM referral letter + DIG (N=24)

Arm 5: Modified Standard letter (N=204)

The utilization will be defined as evidence of dental care through restorations or extractions at the final study visit exam that was previously not found during the baseline exam. All changes will be recorded on a tooth level using ICDAS criteria and then dichotomized at the caregiver level as having obtained or not obtained dental care for their child/children.

There are three treatment comparisons to assess the overall CSM referral letter and DIG: CSM referral letter alone versus standard letter (Arm 1 vs Arm 5), CSM referral letter plus DIG versus standard letter (Arm 2 vs Arm 5), and CSM referral letter alone versus CSM referral letter plus DIG (Arm 1 vs Arm 2). As described below we address the issue of multiple testing, both multiple comparisons and multiple sites, using a gatekeeper approach. By specifying a sequence of tests, this approach will allow for the use of a nominal 0.05 alpha level for each test while maintaining a 0.05 family-wise alpha level for the six tests (three at each study site).

An additional comparison will be conducted to assess the effect of the targeted component (e.g., the ‘timeline’ text): CSM referral letter with and without DIG versus reduced CSM referral letter with and without DIG (Arm 1, 2 vs Arm 3, 4).

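### The entry rule (active ICDAS score of 2 or more) is not tied to the restorative need stated elsewhere, while the primary outcome credits only new restorations or extractions

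*Combined protocol and SAP*

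**What the plan says.** Two descriptions of who is randomized stand side by side.

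- **Lesion score.** Section 5.1: "Caregivers will be randomized if their child has tooth with an International Caries Detection and Assessment System (ICDAS) active lesion score of" 2 or more. Section 4.1 agrees: caregivers whose child has a tooth with an "active lesion score of 2 or greater will be randomized". The exclusions in 5.2 concern only the caregiver's literacy and age.
- **Restorative need or referral.** The protocol summary describes children with restorative treatment needs. Section 4.2 says "Caregivers whose children have no cavities or who have emergent needs will not participate further in the clinical trial" and that "eligible caregivers of children with restorative referrals will be randomized". Section 7.2 says "Randomize caregivers of children with restorative referral outcome on screening to 1 of 5 study arms". Section 8 calls the child's need for restoration a gate: "need for restorative care which is an inclusion/exclusion criterion for study continuation and randomization".

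The primary outcome in 12.2 is "evidence of dental care through restorations or extractions at the final study visit exam that was previously not found during the baseline exam". Section 3.2.1 sends the reader to section 5.2 of the Manual of Procedures (MOP) for examination criteria. It also lists caregiver-reported items, among them "whether the child visited the dentist after the dental screening", as additional surrogate outcomes. They have no part in the arm comparisons of 12.4.

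The planning rates in 12.2 are 19% for the standard letter (earlier school-screening study), 37% for the CSM letter (Medicaid utilization) and 57% for the CSM letter plus guide (caregivers reporting a visit or an appointment in the pilot). The adjustment set in 12.4 is child's age and race, and caregiver SES, education and marital status. Baseline lesion severity is not in it.

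**The concern.** The stated objective is receipt of dental care after a referral. The outcome is narrower: a visit that leads to neither a restoration nor an extraction scores the same as no visit. That is coherent if every randomized child needs a restoration or extraction, and less so if some do not. The documents do not say that an active score of 2 or more amounts to restorative need, so the reader cannot tell which situation holds.

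If such children are in the trial, a caregiver can act on the letter and still be counted as not having obtained care. Rates would fall in every arm, absolute differences would shrink, and the power in 12.2 would be optimistic. The planning rates add to this, because 37% and 57% describe events broader than the one being scored.

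**Working it through.** **Inputs, all from 12.2 unless stated.** Two-sided pooled-variance Z test, alpha 0.05 per test; 102 per arm per site, 204 per arm combined; rates 19%, 37% and 57%; 5% transfers out of school. Section 12.4 tests the standard letter against letter plus guide first, and within each comparison tests the overall effect before the sites.

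**Step 1. Reproduce the plan.** With p̄ the mean of the two rates,

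power = Φ{ [ |p1 − p2|·√n − 1.96·√(2p̄(1 − p̄)) ] / √(p1(1 − p1) + p2(1 − p2)) }.

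For 19% versus 37% at n = 102: (0.18 × 10.0995 − 1.96 × 0.6350) / 0.6221 = 0.92, so power is 82%. For 37% versus 57% it is also 82%. Exactly 80% power needs 97 per arm for either contrast, and 97 × 1.05 = 102, so the plan's figure is consistent with 80% plus a 5% allowance. At n = 204 both contrasts give 98%, as stated.

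**Step 2. Dilution.** Let f be the share of randomized children whose dental care would involve no restoration or extraction. The documents do not give f; the range is an assumption. If these children cannot register the outcome, each rate p becomes p(1 − f). For f = 30%, 19% becomes 13.3% and 37% becomes 25.9%. At n = 102: (0.126 × 10.0995 − 1.96 × 0.5614) / 0.5543 = 0.31, so power is 62%.

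| f | 19 vs 37 becomes | per site / combined | 37 vs 57 becomes | per site / combined | 19 vs 57, per site |
|---|---|---|---|---|---|
| 0 | 19.0 vs 37.0 | 82% / 98% | 37.0 vs 57.0 | 82% / 98% | >99% |
| 10% | 17.1 vs 33.3 | 76% / 97% | 33.3 vs 51.3 | 74% / 96% | >99% |
| 20% | 15.2 vs 29.6 | 70% / 94% | 29.6 vs 45.6 | 66% / 92% | >99% |
| 30% | 13.3 vs 25.9 | 62% / 90% | 25.9 vs 39.9 | 57% / 86% | >99% |

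At f = 50% the lead contrast, 19% versus 57%, still has 94% power per site.

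**Step 3. A milder assumption.** If these children have half the usual chance of registering the outcome, the factor is 1 − f/2. Per-site power for 19% versus 37% is then 79%, 76% and 73% at f = 10%, 20% and 30%.

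**Step 4. Relative risk.** Section 12.4 estimates relative risks. Under this scaling, 0.37(1 − f) / 0.19(1 − f) = 1.95 for every f. The absolute difference is 18 points at f = 0 and 12.6 at f = 30%.

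**The case against.** A reader might infer that children without restorative need are in fact randomized. The documents do not support that as a statement of fact. The summary, 4.2, 7.2 and 8 all point the other way. The inference also needs a meaning for an ICDAS score of 2 and a view on how such a lesion is managed. The documents give neither, and the MOP section that may do so is not among them. What is established is a conflict between entry rules.

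A reader might also infer that a null result could not be told apart from an outcome that could not occur. In the range examined, that does not hold for the lead test or the combined-site tests, which come first in 12.4. Per-site power, taken alone, overstates the loss.

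Two further points stand. The scaling treats 37% and 57% as restoration rates in children who need restorations. They are not, so the table is a sensitivity calculation and not a forecast. A masked clinical examination as primary outcome, with self-report in addition, is a defensible choice, and 3.2.1 already promises to assess the caregiver-reported items.

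None of this removes the conflict. Section 5.1 is the formal inclusion text and words the score as sufficient. Per-site comparisons are among the primary aims in 12.2. The reported-visit items have no specified analysis that would help interpret the primary result.

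**Conclusion.** The point holds as a conflict in the entry wording with a consequence for the outcome. If 4.1 and 5.1 govern, some randomized children may receive dental care that the primary outcome cannot register. If the summary, 4.2, 7.2 and 8 govern, 4.1 and 5.1 are incomplete.

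Under the first reading, the cost falls on precision and interpretation, chiefly in the per-site and adjacent-arm contrasts. At f = 30%, per-site power is 62% and 57%, against 90% and 86% combined. No bias in the relative risk is evident if f is similar across arms, as randomization makes likely. These sizes rest on an assumed f and on affected children having no chance of the outcome; Step 3 shows how far the loss shrinks when the second assumption is relaxed. The recommended changes are worth making whatever f proves to be.

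**What to change.** 1. Add baseline lesion severity (the child's worst ICDAS score) to the prespecified covariates in 12.4. The baseline ICDAS form is already listed among the case report forms in section 13.
2. Prespecify a supportive analysis of the same arm comparisons in children with a restorative referral at baseline. Status is fixed before randomization, so the comparison remains randomized. If every randomized child has such a referral, it coincides with the main analysis and settles the question.
3. Prespecify a supportive outcome of any dental care: a new restoration or extraction at the final examination, or a caregiver-reported visit (2-week questionnaire item 1.1 or final questionnaire item 4.5). Report it beside the unchanged primary outcome.
4. Reconcile 4.1 and 5.1 with the summary, 4.2, 7.2 and 8, so that one entry rule is stated throughout and its relation to the outcome in 12.2 is clear.

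The cost is protocol and analysis-plan wording and one covariate already collected; no visits or forms are added. The drawback is that part of the any-care outcome is self-report, so it should stay supportive.

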5.2 Subject Exclusion Criteria

Exclusion Criteria: Exclusion criteria for Parents/Caregivers:

- Illiterate
- Under 18 years of age

5.3 Strategies for Recruitment and Retention

Subjects will be recruited in Ohio or Washington States and will be volunteers.

Ohio Site: The recruitment follows a 2-stage process (See Section 4.2, Figure 4.2.2): (1) all caregivers of K-4 children enrolled in ECCSD and BCSD will be invited to have their children participate in the dental screening; (2) consented parent/caregivers and assented children will be screened and those who fulfill the inclusion criteria for study continuation and randomization will be randomized. We will follow recruitment strategies that were previously successful working with this minority school-based population (Nelson & Milgrom 2012). The venues for recruitment will include parent-teacher meetings, open house, curriculum nights, health fairs, and at prearranged convenient times during school drop off /pick up of the child. Teacher support will be gained for sending introductory letters and consent forms home to increase recruitment. **Outreach Workers** will be hired from the local community to assist with recruitment at the schools. Candidates will be parent-teacher liaisons who are knowledgeable about the schools and caregivers, and who will foster trust

among caregivers. Based on a previously cited study (Nelson & Milgrom 2012), we expect to recruit 765/889 (86% recruitment rate) from ECCSD. Also based on the previous study, we expect 428/765 recruited children (56% caries rate) will be screened positive for dental caries. Out of the 428, 5% are expected to have acute urgent care needs and be excluded. Further, 10% will be caregivers with multiple children in K-4 and thus will receive the same intervention. A pool of 366 caregivers will be eligible for randomization.

Washington Sites: These sites will use the same recruitment approach as ECCSD. The study intends to recruit 1452/1708 K-4 children (85%). In a recent screening with a similar rural population (Jefferson and Morrow Counties, OR), 85% of families agreed to participate with only a single notice home and no personal contact or follow-up. In an earlier study with a similar rural population, UW investigators recruited 76% of eligible families (Weinstein, Spiekerman & Milgrom 2009). Based on 28% caries rate, we expect that 407/1452 recruited children will be screened positive for untreated caries. 5% of the children who are positive will be excluded because of emergent needs. Further 10% will be caregivers with multiple children. Thus, an available pool of 348 caregivers will be eligible for randomization.

Due to lower than expected enrollment in both the Ohio and Washington sites, we plan a second year of recruitment to include Bedford School District and East Cleveland School District (only KG and perhaps other grades if they did not enroll in the first year). For the Bedford School District, 1274 KG-4th grade children were enrolled during 2015-2016 school year in four elementary schools; 80% Black; 67% economically disadvantaged eligible for free/reduced cost school lunch program. Bedford is quite similar to East Cleveland. Using our experience from the first year of recruitment we expect that out of the 1274 Bedford school children, about 764 will receive baseline screening (60% participation rate). Of 764 children, about 267 caregivers will be randomized (taking into account 30% multiple children and 50% caries rate). Similarly we expect about 50 caregivers will be randomized in East Cleveland. Between Bedford and East Cleveland School Districts, we expect to screen about 950 children in 2016-2017 school year. Of the 950 screened we expect to randomize 317 caregivers. So we can meet our recruitment goal of 258 caregivers that is necessary to complete the study.

